7.8 Definition of Evaluable and Replacement of Study Participants

Participants that discontinue from the study prior to the 4-week post-SBRT blood draw will be considered unevaluable for the analyses of lymphocyte counts and will be replaced. These participants will be evaluable for the tabulation of adverse events.

8. STUDY ASSESSMENTS AND PROCEDURES

8.1 Clinical Assessments

Some data will be accessed via the participant's medical chart or results of diagnostic tests performed as part of the participant's regular medical care. These data may be used for screening or as part of collection of trial data.

8.1.1 Assessment of Adverse Events

Each participant will be evaluated by a licensed clinician at each study visit. The NCI Common Terminology Criteria for Adverse Events (CTCAE) version 5 will be used for the characterization and grading of adverse events.

•

8.1.2 Complete Blood Count (CBC) with Differential

A CBC with differential should be collected and processed at all time-points as designated in the Study Calendar of Assessments in *section 9*.

8.1.3 Concomitant Medications

For this protocol, a prescription medication is defined as a medication that can be prescribed only by a properly authorized/licensed clinician. Medications to be reported in the Case Report Form (CRF) are concomitant prescription medications, over-the-counter medications, and herbal supplements. Whenever possible, corticosteroids/immune modulators should be avoided, especially around the time of CBC or research blood draws, as they can affect the lymphocyte count. If a participant requires any medication listed in the exclusion criteria during or in the 6 months following SBRT, he or she will no longer be followed for the study and no additional blood will be drawn for research purposes. If this occurs within the 4 weeks following SBRT, the patient will be replaced. These medications have been shown to affect the way white blood cells respond to radiation. There are no other prohibited medications related to study participation. Medications should be collected from 28 calendar days before registration through 6 months following SBRT.

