3.3.2 Overall Survival

To overall survival (OS) after lung SBRT for up to 30 months after SBRT.

Endpoints: Overall survival after lung SBRT (every 6 months for the first year, then annually).

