4.1.2 Exclusion Criteria

- 1. Prior history of radiation therapy within 2 years of registration, however radiation therapy for skin cancer is allowed
- 2. Systemic anti-cancer therapy within the last year prior to registration or planned use during or within 6 months post SBRT follow up timeframe (see study calendar).
- 3. Major surgery within the last 30 days before registration and/or planned before the completion of the 6 months post SBRT follow up timeframe (see study calendar).
- 4. Subject is a prisoner.
- 5. Subject is a pregnant woman.
- 6. Subject is not medically able to tolerate the study SBRT treatment of 50-60 Gy in 5 fractions or cannot comply with other aspects of the study including serial bloodwork.
- 7. Subject has HIV, AIDS, any type of hepatitis and/or any blood borne infectious disease for which the research lab cannot receive blood samples.

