For the second aim, repeated measures models will be used to compare the groups with respect to the percentage drop in lymphocyte counts. The stratification factor will be used as a covariate in the model. Contrasts will be used to compare the groups at specific time points, including the 4 week post-treatment time point, where we anticipate there will be the greatest difference between the standard and optimized SBRT groups. The sample size was based on an assumed spatial power covariance structure, but we will consider other covariance matrices as well, such as random effects models. In exploratory analyses will tabulate local control as well as adverse events (see *section 8*) and estimate differences these between groups. Kaplan–Meier curves will be used to summarize overall survival in each of the standard and optimized SBRT groups.

Quantitative analysis of blood counts and radiation dose to the great vessels

We will collect blood, serum and PBMC at baseline and at end of treatment, weeks 4, and 24 after treatment for all study patients. The reference point for post-treatment blood collection will be the start date of radiation therapy to permit intergroup comparisons between the two study arms. This comparison framework was selected based on our available preliminary data, which

suggests that RT-induced lymphocyte effects occur as early as one week following radiation initiation due to the high radiosensitivity of circulating lymphocytes. We will quantify absolute neutrophils, hemoglobin, platelet, and lymphocyte counts for all patients at these time points and compare the changes between the groups and also compare the lymphocyte count results to what was predicted by the simulation algorithm. We will perform a multivariate analysis to identify the correlation between TRL and mean/integral radiation dose to the great vessels. Since substantial circulating blood is also present in the heart and lungs we will also correlate mean heart and lung dose with TRL. Measurement of the magnitude of lymphocyte depletion and correlation with great vessel, lung, and heart integral dose will be performed and compared to the predicted levels for the simulation algorithm.

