7.7 Discontinuation/Withdrawal of Therapy

Participants may withdraw or be discontinued from the study at any time for any of the following reasons:

- Inter-current illness that prevents further treatment
- Subject decides to withdraw from the study
- Unacceptable adverse events(s)
- Requirement of medication listed in the exclusion criteria
- If the investigator feels it is no longer in the participant's interest to continue participation
- Death
- Participant does not comply with study procedures

The primary reason for discontinuation or withdrawal should be entered into OnCore. All participants that discontinue or withdraw from the study will continue to receive standard of care treatment. Participants removed from study treatment for unacceptable adverse events will be followed until resolution or stabilization of the adverse event. Participants who have withdrawn consent will not be followed for any reason.

A participant's participation is considered completed when the subject has received all study treatments and has completed all follow-up procedures (or other milestone to define a completed subject).

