10.2.4 Time Period and Frequency for Event Assessment and Follow-Up

The occurrence of an adverse event (AE) or serious adverse event (SAE) may come to the attention of study personnel during study visits and interviews of a study participant presenting for medical care, or upon review by a study monitor.

All reportable AEs including local and systemic reactions not meeting the criteria for SAEs will be captured on the appropriate case report form (CRF). Information to be collected includes event description, time of onset, clinician's assessment of severity, relationship to study product (assessed only by those with the training and authority to make a diagnosis), and time of resolution/stabilization of the event. All AEs occurring while on study must be documented appropriately regardless of relationship. All AEs will be followed to adequate resolution.

Any medical condition (including a laboratory abnormality) that is present at the time that the participant is screened will be considered as baseline and not reported as an AE. However, if the study participant's condition deteriorates at any time during the study, it will be recorded as an AE. For the purposes of this study, laboratory abnormalities (at baseline or during the study) will not be recorded and are not reportable, except for hematological laboratory abnormalities in a complete blood count (with or without differential), as these are the only laboratory results that have any likelihood of being related to SBRT/study intervention.

Changes in the severity of an AE will be documented to allow an assessment of the duration of the event at each level of severity to be performed. AEs characterized as intermittent require documentation of onset and duration of each episode.

Study staff will record all reportable events with start dates occurring any time after informed consent is obtained until the 6 month visit following SBRT (for non-serious AEs) or anytime (for SAEs considered related to the study intervention). At each study visit, the investigator will inquire about the occurrence of AE/SAEs since the last visit. Events will be followed for outcome information until resolution or stabilization.

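### Read literally, section 8.1.3 ends survival follow-up for participants who need systemic anti-cancer therapy during SBRT or within 6 months after it, so the exploratory survival curves could read too high (minor)

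*Combined protocol and SAP*

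**What the plan says.** The trigger in section 8.1.3 (Concomitant Medications) is: "If a participant requires any medication listed in the exclusion criteria during or in the 6 months following SBRT". The consequence is that "he or she will no longer be followed for the study and no additional blood will be drawn for research purposes". If this happens within 4 weeks after SBRT, the participant is also replaced. The reason given is an effect on how white blood cells respond to radiation.

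Section 4.1.2 names one drug class only: "Systemic anti-cancer therapy within the last year prior to registration or planned use during or within 6 months post SBRT follow up timeframe". Section 7.7 lists the same trigger among the reasons for withdrawal or discontinuation: "Requirement of medication listed in the exclusion criteria".

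OS is an exploratory objective with follow-up to 30 months. The endpoint in section 3.3.2 is "Overall survival after lung SBRT (every 6 months for the first year, then annually)", and the calendar in section 9 allows collection by phone or medical record review. In section 5, Kaplan-Meier "curves will be used to summarize overall survival in each of the standard and optimized SBRT groups". No censoring rule, analysis population or sensitivity analysis is given for OS.

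On safety, section 10.2.4 sets the recording period for non-serious events to end at the 6-month visit, but extends it to "anytime (for SAEs considered related to the study intervention)".

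**The concern.** The removal clause has two parts: the participant is no longer followed, and no more research blood is drawn. If only blood sampling were meant to stop, the first part would add nothing. Staff who apply it as written would stop survival contacts for these participants.

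Participants are clinically node negative and receive SBRT as definitive treatment, and planned systemic therapy within 6 months is already excluded. Unplanned need for it in that window plausibly signals relapse or a new cancer. Kaplan-Meier estimation assumes that those censored have the same later risk of death as those who stay under observation. If follow-up stops because of an event that predicts death, that assumption fails and the curve is too high. The arm curves could also lose comparability if the share removed differed between arms.

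The stated white-cell reason supports ending lymphocyte measurement. It gives no reason to stop recording whether the participant is alive.

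**Working it through.** **1. The passages side by side.**

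| Section | What it implies for a participant who starts systemic therapy at, say, month 4 |
|---|---|
| 8.1.3 | No longer followed; no research blood |
| 7.7 | A listed reason for discontinuation; silent on survival follow-up |
| 3.3.2 and 9 | Survival status every 6 months for a year, then annually, to 30 months; no exception |
| 8.1.4 | Tumor response and hospitalization data run until first recurrence; OS carries no such limit |
| 10.2.4 and 10.2.6 | Related SAEs recorded at any time; all SAEs recorded; no exception |
| 7.8 | Those who discontinue before the 4-week draw leave the lymphocyte analyses but stay evaluable for adverse events; nothing said about OS |

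No section keeps these participants in survival follow-up, and 8.1.3 read literally takes them out.

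**2. Possible size.** The plan states no survival rate, no rate of early systemic therapy and no hazard ratio, so there is no figure of its own to reproduce. All inputs below are assumptions.

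- Survival at 24 months without early systemic therapy: 0.75. Constant monthly hazard λ = −ln(0.75)/24 = 0.01199.
- Share f starting systemic therapy: 5% or 10%, with 20% as an extreme.
- Start of therapy: uniform over months 1 to 6, represented by its mean, r = 3.5 months.
- Death hazard multiplied by HR after the start: 2, 3 or 5.

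True 24-month survival of affected participants is exp{−λ[r + HR × (24 − r)]}:

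- HR 1: 0.750
- HR 2: exp(−0.01199 × 44.5) = 0.587
- HR 3: exp(−0.01199 × 65) = 0.459
- HR 5: exp(−0.01199 × 106) = 0.281

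If these participants are censored when therapy starts, every observed death occurs at hazard λ and the Kaplan-Meier estimate tends to 0.75. True survival over everyone is 0.75 − f × (0.75 − affected survival), so the excess is f × (0.75 − affected survival), in percentage points:

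| f | HR 1 | HR 2 | HR 3 | HR 5 |
|---|---|---|---|---|
| 5% | 0 | 0.8 | 1.5 | 2.3 |
| 10% | 0 | 1.6 | 2.9 | 4.7 |
| 20% | 0 | 3.3 | 5.8 | 9.4 |

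Averaging over the uniform start time instead of using its mean changes no entry by more than about 0.02 points.

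**3. Second check at 30 months.** A large simulation with start times uniform over months 0 to 6 and 30-month survival of 60% or 75% without the trigger gave excesses of 0.7 to 0.9 points (f = 4%, HR 2), 3.2 to 3.6 points (f = 8%, HR 4) and 11.5 to 12.6 points (f = 20%, HR 8). At HR 1 the excess was zero.

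**4. Against sampling error.** With 25 per arm and survival of 0.75, ignoring censoring, the standard error is √(0.75 × 0.25/25) = 0.087. The 95% interval is about ±1.96 × 0.087 = ±0.17, or ±17 points.

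**The case against.** The strongest reply is that 8.1.3 may mean lymphocyte follow-up only. The synopsis speaks of participants being followed for 6 months to assess lymphocytes, and separately of survival being assessed. The rule covers that same 6-month window, is paired with blood draws and rests on a white-cell reason. Section 7.7 bars all follow-up in terms only for one group: "Participants who have withdrawn consent will not be followed for any reason". This reading is tenable. But 8.1.3 does not say so, and section 8.1.4 uses the word follow-up for the full 30 months. The ambiguity stands and is itself a reason to clarify.

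The reply also limits what can be claimed. Three stronger readings are tempting, and the documents do not support them:

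- *Early relapsers leave survival follow-up.* The trigger is needing systemic therapy. Participants who relapse and are managed without it stay in, and those removed contribute time until removal.
- *Late related SAEs are lost.* Sections 10.2.4 and 10.2.6 still require them to be recorded, with no exception for this group. This is a conflict to reconcile; a loss of data is not established.
- *The curves are biased upward by up to 10 points.* The direction needs HR above 1, and the upper end needs 20% affected with HR 5. Nothing in the documents supports that corner.

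A difference between arms in the share removed is possible, since clinicians know the assignment, but no figure in the plan bears on it. Finally, OS is exploratory and only summarized, with no test, power or decision attached, and a bias of 1 to 5 points lies well inside the sampling error. That is a fair argument for low severity. It is no argument for leaving the text as it is, because the bias is avoidable at almost no cost.

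**Conclusion.** The point holds as a minor one. As written, 8.1.3 conflicts with the 30-month survival plan and with the open-ended recording of related SAEs, and no other section resolves the conflict for survival. If the rule is applied literally, and if needing early systemic therapy marks a worse prognosis, censoring is informative and the Kaplan-Meier curves read too high. Under the assumed 5 to 10% affected and HR of 2 to 5, the excess is about 1 to 5 percentage points at 24 months; it is zero at HR 1. These sizes illustrate and do not estimate. Whether the sponsor intended the literal reading cannot be settled from the documents. Neither primary aim, both of which concern lymphocyte counts, is affected.

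**What to change.** - **Section 8.1.3:** replace the clause that ends follow-up with wording that (a) stops research blood, (b) excludes lymphocyte counts taken after systemic therapy starts from the analysis, and (c) continues vital-status follow-up by phone or record review, and the SAE recording already required by 10.2.4, unless consent is withdrawn.
- **Section 7.7:** the phrase to be replaced does not occur here. Add a note that discontinuation for this reason does not end vital-status follow-up.
- **Section 5:** state that OS is not censored at the start of systemic therapy, that censoring is at the date last known alive, and that participants replaced under 8.1.3 remain in the OS curves of their randomized arm.
- **Participants already removed under the rule:** obtain vital status from the medical record where consent allows.

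The cost is a few sentences in an amendment and a small number of phone or record checks by a route already in the calendar. No visit, procedure or treatment changes.

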8.1.4 Review of Medical Record

In this patient population, the following assessments are frequently completed as part of standard clinical care. If they are completed during the timeframes described below, accompanying results should be entered in the designated EDC system as study data.

Assessment	Estimated Timeframe(s)
PET with FDG	Within 8 wks prior to SBRT and if there is a suspicion of tumor recurrence (prior to first recurrence following study participation)
CT scan with contrast	Within 8 wks prior to SBRT and within 24 months after SBRT
Tumor response eval	At SOC intervals until first recurrence during 30 months of follow-up
Hospitalization history	Within 12 wks prior to SBRT and at SOC intervals until first recurrence during 30 months of follow-up

8.2 Research Blood

Research blood will be collected according to the study calendar of assessments in *section 9*. 40 ml of blood will be collected at two time points (pre SBRT and 1 month after SBRT) in green top tubes. Following collection, the blood will be transported at room temperature to [name] laboratory for processing and analysis.

Blood will be analyzed in [name] lab. Research tubes will be labeled directly with a unique identifier ID and associated with the UVA IRB HSR number. All leftover research blood will be stored in [name] lab at UVA once analysis described in the sections below is completed.

8.3 Correlative Studies

In addition to the following, additional assays may be performed for proliferation, function and subtypes depending on study findings.

8.3.1 Lymphocyte functionality in vitro assays

These assays will be run on all participants in both arms at each blood draw time-point.

8.3.2 Lymphocyte Subsets and Activation Phenotypes

The T cell subsets and activation will be measured by flow cytometry using multiple markers to identify T cell subpopulations. The PBMC will be stained for central memory (including but not limited to CD4+/CD45RO+/CCR7-/CD62L+; CD8+/CD45RO+/CCR7-/CD62L+), memory (including but not limited to CD4+/CD45/RO+/CCR7-/CD62L-), and effector (including but not limited to CD4+/CD45RO+/CCR7-/CD27+; CD8+/CD45 RO+/CCR7-/CD27+) CD4+ and CD8+ T cells, CD68 for monocyte, CD33+/CD11b+ for MDSC. Briefly, PBMC will be stained for 30 minutes on ice with the cocktails of fluorescently conjugated monoclonal antibodies (mAbs) or isotype-matched controls, washed twice with Fluorescent Activated Cell Sorting (FACS) buffer. Cells will be analyzed on a FACScalibur (BD Biosciences) and data will be acquired using CellQuest software (BD Biosciences).

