Recent studies have shown a correlation between treatment-induced lymphopenia and inferior survival in patients with glioblastoma, advanced stage non-small cell lung cancer (NSCLC), pancreatic cancer and squamous cell carcinoma of the head and neck^{2,7-10}. In a study published in the *Journal of the National Comprehensive Cancer Network*, investigators collected and analyzed data from 4 independent solid tumor sites from 297 patients with newly diagnosed malignant glioma, resected and un-resected pancreatic cancer, and stage III NSCLC and recorded lymphocyte count, prognostic factors, treatment and survival. They defined treatment related lymphopenia (TRL) as <500 cells/mm³ and found an increased risk for death attributed to TRL in each cohort (gliomas: hazard ratio [HR], 1.8; 95% confidence interval (CI), 1.13–2.87; resected pancreas: HR, 2.2; 95% CI, 1.17–4.12; unresected pancreas: HR, 2.9; 95% CI, 1.53–5.42; lung: HR, 1.7; 95% CI, 0.8–3.61) and in the entire study population regardless of pathologic findings (HR, 2.1; 95% CI, 1.54–2.78; P <.0001). They observed severe TRL in 40% of patients two months after the initiation of chemoradiation and found that it was independently associated with shorter survival from tumor progression¹¹. See *Figure 1*.

RT-induced lymphopenia is likely due to the repeated exposure of radiosensitive lymphocytes to radiation, and possibly the expansion of regulatory T cells and elaboration of immunosuppressive cytokines in response to radiation. Notably, recent data have suggested that lymphocyte subsets exhibit differential sensitivity to radiation, with helper CD4+ T cells being more sensitive than cytotoxic CD8+ T cells in GBM treated with RT and temozolomide², and naïve T cells more sensitive than memory T cells in prostate cancer³. We will test the hypothesis that in optimized SBRT plans, lower lymphocyte depletion may lead to smaller decreases of lymphocyte functions.

[figure not shown]

Figure 1: Relationship between survival and grade III/IV treatment-related lymphopenia in 297 patients with solid tumors.¹¹

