3.3.5 Description of Changes in Lymphocyte Subtypes

Describe the changes in lymphocyte subtypes following SBRT in Arms A and B

Endpoint: Quantity of lymphocyte subtypes (e.g. CD4, CD8) prior to and 4 weeks following SBRT

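### The central memory phenotype in section 8.3.2 is listed as CCR7-negative, like every other T-cell phenotype there, and appears mis-specified; the laboratory should confirm the sign

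*Combined protocol and SAP*

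**What the plan says.** Section 8.3.2 names three kinds of T cell and gives example phenotypes for each.

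- Central memory, CD4 and CD8: "The PBMC will be stained for central memory (including but not limited to CD4+/CD45RO+/CCR7-/CD62L+; CD8+/CD45RO+/CCR7-/CD62L", with CD62L positive in both strings.
- Memory, CD4 only: CD45RO+, CCR7-, CD62L-.
- Effector, CD4 and CD8: "effector (including but not limited to CD4+/CD45RO+/CCR7-/CD27+; CD8+/CD45 RO+/CCR7-/CD27+) CD4+ and CD8+ T cells".

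Each list is worded as non-exhaustive. Section 8.3 adds that "additional assays may be performed for proliferation, function and subtypes depending on study findings".

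The panel serves exploratory objective 3.3.5, whose endpoint is "Quantity of lymphocyte subtypes (e.g. CD4, CD8) prior to and 4 weeks following SBRT". Exploratory objective 3.3.3 relates radiation dose to total lymphocyte count and to the functionality of T-cell subtypes. The background on subset radiosensitivity (Synopsis and section 2) contrasts CD4 with CD8 cells and reports "naïve T cells more sensitive than memory T cells in prostate cancer". Section 8.2 provides the research blood: "40 ml of blood will be collected at two time points (pre SBRT and 1 month after SBRT) in green top tubes".

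**The concern.** A marker is put in a panel to tell subsets apart. CCR7 is written with the same sign in every listed T-cell phenotype, so it does no such work. Central memory and memory then differ only by CD62L. In general immunology usage, central memory T cells express CCR7 together with CD62L, and the absence of CCR7 marks the other memory and effector cells. Read that way, the two central memory strings carry the wrong sign.

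If the laboratory follows the text, a change reported as central memory would concern CCR7-negative cells, while readers would take it to be the conventional subset. Any correlation of that subset with dose under 3.3.3 would carry the same mislabel. The 3.3.5 comparison uses only a pre-treatment and a 4-week sample, and the same label would be applied to both.

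**Working it through.** The plan gives no figure to reproduce. The check is a count of marker combinations against the listed phenotypes.

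**Inputs (section 8.3.2).** The five listed T-cell phenotypes are:

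| Label | Lineage | CD45RO | CCR7 | CD62L | CD27 |
|---|---|---|---|---|---|
| Central memory | CD4 | + | - | + | not used |
| Central memory | CD8 | + | - | + | not used |
| Memory | CD4 | + | - | - | not used |
| Effector | CD4 | + | - | not used | + |
| Effector | CD8 | + | - | not used | + |

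**Step 1: all combinations.** Two lineages and four markers, each positive or negative, give 2 × 2 × 2 × 2 × 2 = 32 combinations. Half, 16, are CCR7+. None of those 16 matches a listed phenotype.

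**Step 2: memory-type (CD45RO+) combinations.** There are 16, of which 8 are CCR7+ and 8 CCR7-.

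| CD45RO+ combinations | Number | Listed as |
|---|---|---|
| CCR7+, any CD62L, any CD27, CD4 or CD8 | 8 | nothing |
| CD4, CCR7-, CD62L+, CD27- | 1 | central memory |
| CD4, CCR7-, CD62L+, CD27+ | 1 | central memory and effector |
| CD4, CCR7-, CD62L-, CD27- | 1 | memory |
| CD4, CCR7-, CD62L-, CD27+ | 1 | memory and effector |
| CD8, CCR7-, CD62L+, CD27- | 1 | central memory |
| CD8, CCR7-, CD62L+, CD27+ | 1 | central memory and effector |
| CD8, CCR7-, CD62L-, CD27+ | 1 | effector |
| CD8, CCR7-, CD62L-, CD27- | 1 | nothing |

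So 0 of 8 CCR7+ combinations are captured. Of the 8 CCR7- combinations, 7 are captured, and 3 of those 7 carry two labels. No CD8 memory phenotype is listed, although the sentence ends by referring to both CD4 and CD8 cells.

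**Step 3: what a sign change alone would do.** With CCR7+ in the two central memory strings, the CD45RO+/CCR7+/CD62L+ combinations are captured: 2 lineages × 2 states of CD27 = 4 of the 8. Both overlaps between central memory and effector disappear, because effector stays CCR7-. The CD4 memory and effector overlap (CD62L-/CD27+) remains, so double labels fall from 3 to 1. There is still no CD8 memory phenotype. The sign change is therefore needed under the usual definition, but it does not complete the scheme.

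These are counts of marker combinations, not proportions of cells. The documents hold no cell frequencies, so the distortion in a reported change cannot be computed.

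**The case against.** A reader might infer that the change in true central memory cells after SBRT is not measured at all. The documents do not support that. The phenotypes are examples, further subtype assays are allowed, and CCR7 is itself in the panel. Where CD45RO, CCR7 and CD62L were stained together, the CCR7+ cells are already in the stored data. Section 8.3.2 speaks of antibody cocktails without saying which antibodies share a tube, so recovery is possible but not assured.

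A reader might also infer that the study's rationale for subset work fails. That does not follow either. The background raises CD4 against CD8 and naïve against memory, not central against effector memory. Objective 3.3.5 gives only CD4 and CD8 as examples, and no objective or section 5 analysis names a central memory result.

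It is also fair to say that the protocol nowhere defines central memory, so the expected sign comes from general knowledge. The documents alone show an uninformative marker and overlapping labels; they do not show which sign the laboratory uses. A text-extraction slip is conceivable, but the same CCR7 sign in all five strings makes it unlikely.

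These points narrow the concern without removing it. Non-exhaustive wording allows more phenotypes to be added; it does not correct a named phenotype that carries the wrong label.

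**Conclusion.** The point holds as a minor error in an operative assay definition. From the text alone, CCR7 separates none of the listed subsets, no listed phenotype captures CCR7+ memory cells, and three marker combinations carry two labels. Given the usual CCR7+/CD62L+ definition, which is the one outside assumption here, the central memory strings appear mis-specified, and a result reported under that label would describe CCR7-negative cells.

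The consequence is confined to descriptive exploratory work under 3.3.5, and to 3.3.3 if these subsets are used there. Both primary objectives rest on lymphocyte counts, so their endpoints, the sample size and the power are untouched. If the laboratory intends a CCR7-negative definition, the label needs a stated justification, and the overlaps still need to be resolved.

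**What to change.** 1. Ask the laboratory to confirm the intended CCR7 sign for central memory.
2. Unless a CCR7-negative definition is deliberate and justified in the text, change the two strings in section 8.3.2 to CD4+/CD45RO+/CCR7+/CD62L+ and CD8+/CD45RO+/CCR7+/CD62L+.
3. State memory and effector phenotypes that are mutually exclusive, for both CD4 and CD8 cells.
4. Re-analyse files already acquired with the corrected phenotypes wherever CD45RO, CCR7 and CD62L were stained in the same tube. Where they were not, report the subset under its actual markers and not as central memory.

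The cost is a short text amendment and some analysis time on stored flow files. Where the three markers were stained together, no new reagent, blood draw or visit is needed.
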